### **3.6. HIV Resistance Monitoring**

Plasma samples for HIV resistance testing will be collected from subjects who experienced HIV virologic rebound. Following the unconfirmed HIV virologic rebound, confirmation should be performed as soon as possible but within 2 weeks after determination of initial observation. If HIV rebound is confirmed, the samples will be used for HIV-1 genotype/phenotype testing.

### **3.7. Treatment Discontinuations Criteria**

The Medical Monitor should be consulted prior to subject discontinuation when medically feasible. Study medication may be discontinued in the following instances:

- Unacceptable toxicity, as defined in Section 7 of the protocol, or toxicity that, in the judgment of the investigator, compromises the ability to continue study-specific procedures or is considered to not be in the subject's best interest
- Pregnancy of female subject, or of female partner of male subject
- HCV efficacy failure as defined in Section 3.3.
- Significant protocol violation including non-compliance with study assessments.
- Subject request to discontinue for any reason; it is important to determine whether the withdrawal of consent is primarily due to an AE, lack of efficacy or other reason.
- Discontinuation of the study at the request of Gilead, regulatory agency or an Institutional Review Board (IRB)/Independent Ethics Committee (IEC)

If a subject meets discontinuation criteria during treatment, an early termination visit will be required (Section 6.2.5). All subjects should complete the 4-week Post-treatment visit.

### **3.8. Discontinuations**

Subjects discontinuing treatment prior to completion of the assigned dosing period should complete an Early Termination visit (see Section 6.2.4). All subjects should also complete a 4-Week Post Treatment visit. Subsequent visits will be determined by the virologic response to treatment as outlined in Section 3.3.

If GS-7977 is discontinued, subjects should discontinue ribavirin. Under no condition should the subject remain on ribavirin monotherapy.

### **3.9. Pharmacogenomic Substudy**

All subjects will be eligible to participate in the Pharmacogenomic Substudy. A blood sample should be drawn at the Baseline/Day 1 visit. Subjects must sign a separate informed consent to participate in this Substudy. If not obtained at Baseline/Day 1, the sample may be drawn at any time during the study.

### **3.10. Registry Studies**

#### **3.10.1. Sequence Registry Study**

Subjects who do not achieve SVR as well as those who achieve SVR and later become detectable will be eligible for enrollment in the Sequence Registry Study. The purpose of the Sequence Registry Study will be to monitor the persistence of resistant mutations for up to 3 years after the last dose of study medication. The Sequence Registry Study is described in a separate protocol (GS-US-248-0123).

#### **3.10.2. SVR Registry Study**

Subjects who achieve SVR at 24-weeks post treatment will be eligible for enrollment in the SVR Registry Study. The purpose of the SVR Registry Study will be to evaluate durability of SVR for up to 3 years post-treatment. The SVR Registry Study is described in a separate protocol (GS-US-248-0122).

## 4. SUBJECT POPULATION

### 4.1. Number of Subjects and Subject Selection

Approximately 230 subjects will be enrolled in this study consisting of 115 treatment naïve genotype 1 subjects and 115 treatment naïve and treatment experienced genotype 2/3 subjects. In order to manage the total study enrollment, Gilead Sciences, Inc., at its sole discretion, may suspend screening and/or enrollment at any site or study-wide at any time.

### 4.2. Inclusion Criteria

Subjects must meet *all* of the following inclusion criteria to be eligible for participation in this study.

1. Willing and able to provide written informed consent
2. Male or female, age  $\geq 18$  years with chronic HCV and HIV-1 infection
3. HCV RNA  $\geq 1 \times 10^4$  IU/mL at Screening
4. Infection with HCV genotype 1, 2 or 3 as determined at Screening
5. HIV-1 infection confirmed with positive ELISA and Western blot at Screening (if necessary)
6. The subject's medical records must be sufficient to be categorized on IFN eligibility or prior treatment with PEG/RBV into one of the following categories as defined in Section 6.4.2:

a) **Treatment Naïve - IFN-eligible**

b) **Treatment Naïve - IFN-ineligible:**

Subjects treated in the Drug Interaction portion (Part A) of the P7977-1910 protocol will be considered treatment-naïve.

c) **Treatment Experienced - IFN Intolerant (genotype 2/3 only)**

d) **Treatment Experienced - Non-Response (genotype 2/3 only)**

e) **Treatment Experienced - Relapse/Breakthrough (genotype 2/3 only)**

7. Confirmation of chronic HCV infection documented by either:
  - a positive anti-HCV antibody test or positive HCV RNA or positive HCV genotyping test at least 6 months prior to the Baseline/Day 1 visit, or

- a liver biopsy performed prior to the Baseline/Day 1 visit with evidence of chronic HCV infection
8. Ability to determine the presence/absence of cirrhosis
- a) Cirrhosis is defined as any one of the following:
- Liver biopsy within 2 years of screening showing cirrhosis
  - A FibroTest® score of >0.75 AND an AST:platelet ratio index (APRI) of >2 performed during screening
- b) Absence of cirrhosis is defined as any one of the following:
- Liver biopsy within 2 years of Screening showing absence of cirrhosis
  - A FibroTest® score of  $\leq 0.48$  AND APRI of  $\leq 1$  performed during Screening

In the absence of a definitive diagnosis of presence of cirrhosis by the above criteria, a liver biopsy is required.

If both a biopsy and FibroTest® plus APRI results are obtained, the liver biopsy results will supersede for the determination of cirrhosis.

9. HIV antiretroviral therapy (ARV) criteria of one of the following:
- a) ARV untreated, for  $\geq 8$  weeks preceding the Screening visit, with a CD4 T-cell count  $>500$  cells/mm^3 [up to 10% of study subjects may be ARV untreated], or
- b) On a stable, protocol-approved, ARV for  $>8$  weeks prior to Screening with a CD4 T-cell count  $>200$  cells/mm^3 and a documented undetectable plasma HIV-1 RNA level for  $\geq 8$  weeks by local assay preceding the Screening visit. HIV-1 RNA levels should be measured within 1 year of the Screening visit. Screening HIV RNA must be  $< 50$  cp/mL as measured by the COBAS AMPLIPREP/COBAS TaqMan 2.0 HCV RNA assay.
- Subjects who switched from atazanavir/ritonavir (boosted) to darunavir/ritonavir (boosted) prior to Amendment 2 will be exempt from the 8 week stable ARV regimen requirement as defined in Section 6.4.2.
- c) HIV antiretroviral medications allowed in this study include the following and should be administered per the prescribing information in the package insert:
- emtricitabine/tenofovir plus:
    - atazanavir/ritonavir (boosted); or
    - darunavir/ritonavir (boosted); or

- efavirenz; or
- raltegravir; or
- rilpivirine

Alternative combinations of the above listed medications may be allowed on a case by case basis. ARV regimens not on the above list are excluded from this study.

10. Body mass index (BMI)  $\geq 18 \text{ kg/m}^2$
11. Screening ECG without clinically significant abnormalities as determined by the investigator
12. Subjects must have the following laboratory parameters at screening:
  - a) ALT  $\leq 10 \times$  the upper limit of normal (ULN)
  - b) AST  $\leq 10 \times$  ULN
  - c) Hemoglobin  $\geq 12 \text{ g/dL}$  for male,  $\geq 11 \text{ g/dL}$  for female subjects
  - d) INR  $\leq 1.5 \times$  ULN unless subject has known hemophilia or is stable on an anticoagulant regimen affecting INR
  - e) Albumin  $\geq 3 \text{ g/dL}$
  - f) Direct bilirubin  $\leq 1.5 \times$  ULN
    - For subjects receiving an atazanavir/ritonavir (boosted) regimen, a direct bilirubin  $> 1.5 \times$  ULN will be allowed if  $< 25\%$  of the total bilirubin.
  - g) HbA1c  $\leq 10\%$
  - h) Creatinine clearance ( $CL_{cr}$ )  $\geq 60 \text{ mL/min}$ , as calculated by the Cockcroft-Gault equation {2202}
13. Subject has not been treated with any investigational drug or device within 30 days of the Screening visit
14. A female subject is eligible to enter the study if it is confirmed that she is:
  - a. Not pregnant or nursing
  - b. Of non-childbearing potential (i.e., women who have had a hysterectomy, have both ovaries removed or medically documented ovarian failure, or are postmenopausal – women  $> 50$  years of age with cessation (for  $\geq 12$  months) of previously occurring menses), or

- c. Of childbearing potential (i.e., women who have not had a hysterectomy, have not had both ovaries removed, or no medically documented ovarian failure). Women  $\leq$  50 years of age with amenorrhea will be considered to be of childbearing potential. These women must have a negative serum pregnancy test at Screening and a negative urine pregnancy test on the Baseline/Day 1 visit prior to randomization. They must also agree to one of the following from 3 weeks prior to Baseline/Day 1 until 6 months after last dose of RBV:

- Complete abstinence from intercourse. Periodic abstinence from intercourse (e.g., calendar, ovulation, symptothermal, post-ovulation methods) is not permitted.

Or

- Consistent and correct use of 1 of the following methods of birth control listed below in addition to a male partner who correctly uses a condom from the date of Screening until 6 months after the last dose of RBV. Women of childbearing potential must not rely on hormone-containing contraceptives as a form of birth control during the study. Female subjects using a hormone-containing contraceptive prior to Screening may continue their contraceptive regimen in addition to the study specified methods of birth control.
  - intrauterine device (IUD) with a failure rate of  $< 1\%$  per year
  - female barrier method: cervical cap or diaphragm with spermicidal agent
  - tubal sterilization
  - vasectomy in male partner

15. All male study participants must agree to consistently and correctly use a condom, while their female partner agrees to use either 1 of the non-hormonal methods of birth control listed above or a hormone-containing contraceptive listed below, from the date of Screening until 7 months after their last dose of RBV:

- implants of levonorgestrel
- injectable progesterone
- oral contraceptives (either combined or progesterone only)
- contraceptive vaginal ring
- transdermal contraceptive patch

16. Male subjects must agree to refrain from sperm donation for at least 7 months after the last dose of RBV.
17. Subject must be of generally good health as determined by the Investigator.
18. Subject must be able to comply with the dosing instructions for study drug administration and able to complete the study schedule of assessments.
19. Liver imaging within 6 months of Baseline/Day 1 is required in cirrhotic patients only, to exclude hepatocellular carcinoma (HCC)

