- In the absence of a definitive diagnosis of presence or absence of cirrhosis by the above criteria, a liver biopsy is required during screening. If both a biopsy and FibroTest® plus APRI results are obtained, the biopsy results will supersede for the determination of cirrhosis.
- HIV antiretroviral therapy (ARV) criteria of one of the following:
  - ARV untreated for  $\geq 8$  weeks preceding the Screening visit with a CD4 T-cell count  $>500$  cells/mm^3 [up to 10% of study subjects may be ARV untreated], or
-

- 
- On a stable, protocol-approved, ARV for >8 weeks prior to Screening with a CD4 T-cell count >200 cells/mm^3 and undetectable plasma HIV-1 RNA level by local assay for  $\geq 8$  weeks preceding the Screening visit. HIV-1 viral load results should be measured within 1 year of the Screening visit. Screening HIV RNA must be < 50 cp/mL as measured by the COBAS AMPLIPREP/COBAS TaqMan 2.0 HCV RNA assay.
    - Subjects who switched from atazanavir/ritonavir (boosted) to darunavir/ritonavir (boosted) prior to Amendment 2 will be exempt from the 8 week stable ARV regimen requirement as defined in Section 6.4.2.
  - HIV antiretroviral medications allowed in this study include the following and should be administered per the prescribing information in the package insert:
    - emtricitabine/tenofovir plus:
      - atazanavir/ritonavir (boosted); or
      - darunavir/ritonavir (boosted); or
      - efavirenz; or
      - raltegravir; or
      - rilpivirine

Alternative combinations of the above listed medications may be allowed on a case by case basis. ARV regimens not on the above list are excluded from this study.

- Body mass index (BMI)  $\geq 18$  kg/m^2
  - Subjects must have the following laboratory parameters at Screening:
    - ALT  $\leq 10 \times$  the upper limit of normal (ULN)
    - AST  $\leq 10 \times$  ULN
    - Hemoglobin  $\geq 12$  g/dL for male,  $\geq 11$  g/dL for female subjects
    - INR  $\leq 1.5 \times$  ULN unless subject has known hemophilia or is stable on an anticoagulant regimen affecting INR
    - Albumin  $\geq 3$  g/dL
    - Direct bilirubin  $\leq 1.5 \times$  ULN
      - For subjects receiving an atazanavir/ritonavir (boosted) regimen, a direct bilirubin  $> 1.5 \times$  ULN will be allowed if <25% of the total bilirubin.
-

---

Diagnosis and Main  
Eligibility Criteria:  
(Continued)

- HbA1c  $\leq$  10%

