- Creatinine clearance ( $CL_{cr}$ )  $\geq$  60 mL/min as determined by Cockcroft-Gault {2202}
- Agree to use two forms of highly effective contraception, as referenced in Section 4.2, for the duration of the study and for 6 months (7 months for males) after the last dose of study medication. Females of childbearing potential must have a negative pregnancy test at Screening and Baseline

Subjects will be ineligible if they meet any of the following criteria:

- Non-genotype 1/2/3 or mixed genotype at Screening
  - Genotype 1 subjects who have received prior HCV treatment
  - Poor control with ARV therapy requiring a modification of therapy within 1 month of GS-7977 dosing.
  - Prior exposure to a direct-acting antiviral targeting the HCV NS5B polymerase. Subjects participating in the Drug Interaction (part A) of P7977-1910 protocol are an exception to this criterion
  - Evidence or history of hepatic decompensation
  - Hematologic or biochemical parameters at screening outside the protocol-specified requirements
  - Screening ECG with clinically significant abnormalities as determined by the investigator
  - Chronic hepatitis B virus (HBV) infection
  - Hepatocellular carcinoma or other malignancy (with exception of certain resolved skin cancers)
  - Chronic use of systemic immunosuppressive agents or immunomodulatory agents
  - Active or recent history ( $\leq$  1 year) of drug or alcohol abuse
  - A new AIDS-defining condition diagnosed within 30 days prior to screening
  - Active, serious infection (other than HIV-1 or HCV) requiring parenteral antibiotic or antifungal therapy within 30 days prior to Baseline
  - History or current evidence of any condition, therapy, laboratory abnormality or other circumstance that might confound the results of the study, or interfere with the subject's
-

participation for the full duration of the study, such that it is not in the best interest of the subject to participate

See Sections 4.2 and 4.3 of the protocol for full inclusion/Exclusion criteria.

---

Study Procedures/  
Frequency:

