### 6.1. Screening Assessments

#### 6.1.1. Screening Visit (Day -28 to Day 1)

Subjects will complete all screening assessments within 28 days of the Baseline/Day 1 visit. The screening window can be extended to 42 days for subjects requiring biopsy or in extenuating circumstances.

The following procedures will be performed and documented:

- Obtain signed informed consent
  - A separate informed consent will be required from subjects participating in the pharmacogenomic substudy.
- Obtain medical history
- Obtain information on prior HIV treatments
- Obtain information on IFN eligibility and prior treatment history with PEG-IFN as per Section [6.4.2](#). The following are the required source documents and medical information required for each of the defined criteria by genotype and treatment arm (redacted data to be provided to the sponsor prior to enrollment):
  - IFN Eligibility
    - Treatment naïve Genotype 1, 2 and 3
    - A redacted source document confirming IFN eligibility or ineligibility must be received and approved by the Sponsor/CRO prior to the subject being enrolled.

- IFN Intolerance
  - Treatment experienced Genotype 2 and 3 only
  - Start dates and stop dates for treatment with PEG-IFN (and RBV if applicable)
  - A redacted source document confirming IFN intolerance must be received and approved by the Sponsor/CRO prior to the subject being enrolled.
- Viral Response Data
  - Treatment experienced Genotype 2 and 3 only
  - In order to categorize the subject's prior response as either Non-Response or Relapse/Breakthrough, the following information must be provided to the Sponsor/CRO prior to enrollment:
    - Prior Treatment Dates (start and stop)
    - Prior Viral Response Data
    - HCV RNA assay
      - RT-PCR, TMA or bDNA
      - Undetectable as <LLOQ, BLOQ or <LLOD
- Cirrhosis determination as per Section 4.2
  - If the presence of cirrhosis is determined, then appropriate diagnostic imaging (CT or Ultrasound) should be performed to exclude the presence of hepatocellular carcinoma (HCC)
- Obtain details of concomitant medications and adverse events
- Perform complete physical examination including vital signs, body weight, and height.
- Perform 12-lead ECG
- Obtain blood samples for safety testing as well as:
  - HCV RNA
  - HIV RNA
  - CD4 T-lymphocyte Absolute Count and %
  - Determination of HCV viral genotype
  - HCV antibody, HIV 1/2 antibody, and HBs antigen

- HbA1c
- TSH
- IL28B

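### Section 4.2 item 8 drops the words for absence from its biopsy rule and, read literally, sends subjects already classed as non-cirrhotic by FibroTest/APRI to liver biopsy

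*Combined protocol and SAP*

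**What the plan says.** Criterion 8 in protocol Section 4.2 is headed "Ability to determine the presence/absence of cirrhosis". Part (a) gives two routes to a finding of cirrhosis: a biopsy within 2 years of screening, or FibroTest >0.75 together with APRI >2. Part (b) opens "Absence of cirrhosis is defined as any one of the following" and lists a biopsy within 2 years showing no cirrhosis, or FibroTest ≤0.48 together with APRI ≤1 during screening. Either route is enough. Then comes the biopsy rule: "In the absence of a definitive diagnosis of presence of cirrhosis by the above criteria, a liver biopsy is required". A closing sentence settles conflicts: if both a biopsy and FibroTest "plus APRI results are obtained, the liver biopsy results will supersede for the determination of cirrhosis".

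The synopsis sets out the same definitions under its main eligibility criteria, but its biopsy rule reads: "In the absence of a definitive diagnosis of presence or absence of cirrhosis by the above criteria, a liver biopsy is required during screening".

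Two cross-references lead to Section 4.2. The synopsis ends its criteria with "See Sections 4.2 and 4.3 of the protocol for full inclusion/Exclusion criteria", and the screening procedures in Section 6.1.1 list "Cirrhosis determination as per Section 4.2". Section 6.1.1 also says: "The screening window can be extended to 42 days for subjects requiring biopsy or in extenuating circumstances".

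**The concern.** The rule in Section 4.2 is triggered whenever cirrhosis has not been shown to be present. A subject shown not to have cirrhosis by the non-invasive route in 8(b) meets that trigger, so one sentence classifies the subject and the next orders a biopsy. The biopsy result would then override the FibroTest/APRI result. Taken at its word, the text leaves the non-invasive route to a non-cirrhotic classification with no use of its own.

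What is at stake is an invasive procedure. A site or monitor applying Section 4.2 as written would either require a biopsy that the synopsis does not call for, or treat its absence as a deviation. The point has more weight because item 12(d) of the same section waives the INR limit for subjects with known hemophilia or on stable anticoagulation, in whom an unneeded biopsy is least welcome. The issue concerns patient burden and eligibility conduct, not the efficacy analysis.

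**Working it through.** No figure in the plan needs reproducing. The check is a comparison of two rules over every possible screening state.

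**Inputs** (Section 4.2 item 8, and the synopsis eligibility criteria)
- Biopsy within 2 years: none; showing cirrhosis; showing no cirrhosis.
- FibroTest/APRI at screening: presence (>0.75 and >2); absence (≤0.48 and ≤1); indeterminate (every other combination).
- Where both are available, the biopsy decides.

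Number of states: 3 × 3 = 9.

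**Rules compared**
- Synopsis: new biopsy if neither presence nor absence is established.
- Section 4.2: biopsy if presence is not established. Unlike the synopsis, this sentence does not say the biopsy must be done during screening, so one already done within 2 years is taken to satisfy it.

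| Biopsy within 2 years | FibroTest/APRI | Synopsis | Section 4.2, literal |
|---|---|---|---|
| None | Presence | No new biopsy | No new biopsy |
| None | Absence | No new biopsy | **Biopsy** |
| None | Indeterminate | Biopsy | Biopsy |
| Cirrhosis | Any of 3 | No new biopsy | No new biopsy |
| No cirrhosis | Any of 3 | No new biopsy | No new biopsy (existing one counts) |

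**Result:** 1 state requires a new biopsy under the synopsis and 2 under Section 4.2. Difference: 2 − 1 = 1 state, namely no recent biopsy with FibroTest ≤0.48 and APRI ≤1.

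**Sensitivity to the assumption:** if an existing biopsy showing no cirrhosis did not count as the required biopsy, the last row would add 3 states. Section 4.2 would then require a biopsy in 2 + 3 = 5 states, and the difference would be 5 − 1 = 4. The affected state above is in the difference under either reading.

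**Evidence of intent:** four places point to the synopsis rule as the intended one. The heading of item 8 names both outcomes; 8(b) makes FibroTest/APRI sufficient for absence; the synopsis has the full sentence; and Section 6.1.1 treats subjects needing a biopsy as a subset. In addition, Appendix 2 Tables 1 and 2 schedule FibroTest/APRI at screening for everyone and have no row for biopsy.

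**Screening time:** the permitted window for a subject sent to biopsy grows from 28 to 42 days, 42 − 28 = 14 days. This is an allowed maximum, not an expected delay.

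**The case against.** The strongest reply is that the protocol corrects itself. The heading, item 8(b), the synopsis and the screening schedules all point one way, and a careful reader would not biopsy a subject whom 8(b) has just classified. That is true, and it is why the repair is safe. It does not make the sentence right: an instruction about an invasive procedure should not depend on the reader noticing that it contradicts the line above it.

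A second reply is that no clause ranks the body of the protocol above the synopsis; the synopsis refers to Section 4.2 for the full criteria, which speaks to completeness rather than precedence. This stands as far as it goes. But Section 6.1.1 sends sites to Section 4.2 for this determination, and Section 4.2 requires all its criteria to be met, so the defective sentence is the one in use at screening.

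A third reply is that the count of one state depends on letting an older biopsy satisfy the rule, and that counting states says nothing about numbers of subjects. Both remarks are fair. The assumption follows from the Section 4.2 sentence, which sets no time for the biopsy, but it has to be stated. The count shows where the texts diverge, not how often.

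Finally, the harm is not demonstrated: the documents show no site that misapplied the text and no deviation recorded for it. That stands too, and it limits the weight of the point.

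**Conclusion.** The concern holds. Section 4.2 item 8 is wrong as written and conflicts with both the synopsis and its own part (b). The two rules differ in one of nine screening states, given that a biopsy within 2 years meets the Section 4.2 requirement.

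How many subjects fall in that state cannot be worked out from the documents. As context only, if about 20% of 230 enrolled subjects are cirrhotic as planned, 230 × 0.80 = 184 are not; the affected subjects are an unknown part of that group, plus any who are screened and not enrolled.

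The correction should be made, because it governs an invasive procedure and costs almost nothing. It does not put the trial's conclusions at risk: the SVR12 endpoint, the sample size and the analyses in the SAP do not depend on it.

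**What to change.** Replace the biopsy sentence in Section 4.2 item 8 with the synopsis sentence: "In the absence of a definitive diagnosis of presence or absence of cirrhosis by the above criteria, a liver biopsy is required during screening". Carry the same wording into any eligibility checklist or monitoring guide drawn from Section 4.2.

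The cost is one sentence, with no change to visits, sample size or analyses. Under Section 10.2.1 a protocol modification needs IRB or IEC approval before use, and about 45 sites are planned, so the sensible vehicle is the next amendment. If enrolment has already closed, as the SAP's September 2013 date for the last post-treatment Week 12 visits in Groups 1 and 3 would suggest for those groups, a written clarification for eligibility and deviation review would serve. It should state that a subject meeting 8(b) by FibroTest and APRI needed no biopsy.
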